7.4 Missed Follow-up Visits

If a subject refuses to return for any follow-up visit, the investigator or research personnel will attempt to obtain at least vital status and whether or not the subject has experienced episodes of AF. A Protocol Deviation eCRF will be completed for each missed visit. The investigator will remain responsible for subject follow-up and data integrity. A subject may be exited from the study if he/she has missed two consecutive follow-up appointments. However, 3 documented attempts by investigator and study staff must be made prior to subject withdrawal. An escalation of the follow-up attempts should be used at the site's discretion. Escalation includes telephone calls, certified letters, email notification, and calls to family members.

7.5 Subject Withdrawal or Lost to Follow-up

A subject may voluntarily withdraw from the study at any time. The investigator and research staff should encourage all subjects to return for the Protocol required follow-up visits. If a subject refuses study follow-up, he/she should be encouraged to be followed by a physician per the standard of care and the investigation site should attempt to collect vital status and study related adverse events.

The investigator may also withdraw the subject's participation in the study.

A subject will be considered lost to follow-up and terminated from the study by the Sponsor once the subject has missed two consecutive follow-up appointments and three documented attempts have been made by the investigator to contact the subject or subject's relatives to schedule each appointment. One of the three documented attempts must include a certified letter. The Investigator must complete the appropriate eCRF documenting the subject's termination from the clinical study.

7.6 Bias Control Measures - Core Laboratory Data Analysis

7.6.1 Cardiac CT/MR

A cardiac core laboratory will be utilized to allow for the objective evaluation of pre- and post-procedure CT/MR imaging. Evaluations of these images will be performed by the core lab's technical personnel trained in the evaluation of the images to detect the presence or absence of pulmonary vein stenosis per the core lab protocol. The core lab will provide an imaging protocol for each type of imaging test listed in the protocol. Uniformity of these tests maximizes the accuracy of the comparison between the pre- and post-procedure results of each subject and comparison of test results between sites. A baseline cardiac CT/MR (performed within 3 months of the study procedure) must be completed for each study subject and submitted to the cardiac core laboratory for comparison to the study-required CT/MR image/s.

7.6.2 Holter Monitoring and Event Recording

A core laboratory will be used to evaluate the events obtained from the 24-hour Holter monitors and ECG data at the 6 and 12 month follow-up visits for recurrence of an atrial arrhythmia (atrial fibrillation, atrial flutter or atrial tachycardia) episode. Initial

evaluations will be done by a technical person trained in the evaluation for these tests and the initial evaluations will be affirmed by a physician.

In addition to the clinical sites following the study subjects, the core lab also will track the subjects to ensure that each subject remains active in the use of their event monitor.

Subjects will be provided a TTM monitor at the 90-day visit. The core lab will create and provide copies of the required TTM schedules for subjects to transmit their weekly and monthly transmissions in accordance with the protocol requirements. Subjects are required to submit asymptomatic readings weekly for 8 weeks following the blanking period, then once a month on a monthly basis for the remainder of the study. Study subjects also will be instructed to use the event monitor at any time following their 90 day through day 365 follow up visit for any recurrence of their symptoms. The core lab will accept subject transmission 24 hours a day and 7 days per week. If a study subject misses their scheduled transmission, the core lab will contact the site until the subject is reached and a transmission has been received.

Study subjects will be considered compliant with the use of the TTM device if they transmit within ± 3 days of their scheduled transmission date and achieve at least 80% of their scheduled transmissions. If the TTM compliance rate is less than 80%, it will be considered as a major protocol deviation.

7.7 Clinical Events Committee

A committee of physicians, with a specialty related to the study procedure and not associated with Hansen Medical will be selected as the Clinical Events Committee (CEC) for this trial. Responsibilities of the CEC are listed below:

- The approval of specific criteria used to define and categorize clinical events and clinical endpoints in the study in conjunction with the Sponsor.
- Reviewing and adjudicating all investigator-indicated device-related adverse events and all adverse events that have the potential to be Major Complications, including the occurrence of early onset events 7 days post ablation procedure) and the incidence of esophageal injury and pulmonary vein stenosis through 180 days.
- Review and adjudicate the following potential Major Complications (Section 7.8.3) that occur within 7 days of the ablation procedure, including:
 - Death,
 - Stroke,
 - Myocardial infarction,
 - Diaphragmatic paralysis,
 - Transient ischemic attack (TIA),
 - Cardiac tamponade,
 - Pericarditis,
 - Pneumothorax,
 - Hospitalization or emergency room visit,

- Vascular access complications,
 - Heart block,
 - Pulmonary edema,
 - Pericardial effusion resulting in pericardiocentesis or surgical intervention,
 - Thromboembolism.
- Review and adjudicate the occurrence of pulmonary vein stenosis or atrio-esophageal fistula through day 180.
 - Review and adjudicate adverse events reported as possibly/probably device-related.
 - Re-adjudicate events in question or when data subsequently changes or new data become available.
 - See **Appendix L** for a definition of all Major Complications.

7.8 Adverse Events

Adverse events (AEs) are defined as any unfavorable and unintended sign, symptom, or disease possibly associated with the study procedure, study device or required study testing. This does not imply that there is a relationship between the adverse event and the device under investigation. All AEs will be recorded onto the Electronic Data Capture (EDC) case report form for visits (post procedure) documented in the permanent medical record. The investigator is ultimately responsible for reporting AEs to the Sponsor. The investigator will evaluate the AE in detail, including the date of onset, description, severity, duration, outcome, and causality as specified in this section.

Intensity or Severity of an Adverse Event:

The intensity or severity of each AE must be assessed according to the following classification:

Table 10: Adverse Event Severity

Mild	An event that results in minimal transient impairment of a body function or damage to a body structure, and/or does not require intervention other than monitoring.
Moderate	An event which results in moderate transient impairment of a body function or damage to a body structure, or which requires intervention, such as the administration of medication or cardioversion, to prevent permanent impairment of body function or damage to body structure.
Severe	An event which is life threatening, which results in a permanent impairment of a body function or damage to a body structure, or which requires significant intervention, such as the major surgery, to prevent permanent impairment of body function or damage to body structure.

Outcome:

The outcome of each AE must be assessed according to the following classification:

Table 11: Adverse Event Outcome

Resolved	Subject fully recovered with no observable residual effects.
Improved	Subject's condition improved, but residual effects remain.
Unchanged	AE is ongoing.
Worsened	Subject's overall condition worsened.
Death	Subject died as a result of the AE (whether or not the AE is related to the investigational device or procedure).

Causality:

The causality of each AE must be assessed according to the following classification:

Table 12: Adverse Event Causality

Device –related	The investigational device directly caused or contributed to the AE.
Possibly device related	The investigational device may have caused or contributed to the AE.
Procedure related	The event is directly associated by timing and/or is pathophysiologic with standard electrophysiology or ablation procedure described in this protocol.
Possibly procedure related	The event may be associated by timing and/or is pathophysiologic with standard electrophysiology or ablation procedure described in this protocol.
Not related	The event is not associated with the investigational device or the procedure described in this protocol.

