5.2 Primary Safety Endpoints

The primary safety endpoint is defined as the incidence of Major Complications, as defined below:

Major Complications during the procedure through 7 days:

- Death
- Stroke
- Myocardial Infarction
- Diaphragmatic paralysis
- Transient Ischemic Attack (TIA)
- Cardiac Tamponade
- Pericarditis
- Pneumothorax
- Hospitalization or Emergency Room Visit
- Vascular Access Complication
- Heart Block
- Pulmonary Edema
- Pericardial Effusion resulting in pericardiocentesis or surgical intervention
- Thromboembolism

Major Complications during the procedure through 180 days:

- Pulmonary vein stenosis
- Atrio-esophageal fistula

Major Complication definitions can be found in **Appendix L** of this protocol. All Major Complications, as reported by the clinical investigator, will be reviewed and adjudicated by the Clinical Events Committee (CEC).

All adverse events will be documented and collected once the informed consent has been signed.

In the event of a study subject death, all possible efforts will be made to obtain relevant records from the hospital or the subject's primary care physician, including death certificates, to determine the cause of death.

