7.8.3 Major Complications

Major Complications are adverse events which may occur in conjunction with or following atrial ablation that are included in the primary safety endpoint for this study. The list and definitions for adverse events that are considered Major Complications are outlined in **Appendix L**.

Should a Major Complication occur, the investigator is required to report by eCRF all available information regarding the Major Complication to the Sponsor promptly upon learning of the event. Additional time may be required in order to obtain the background details related to a Major Complication; however, the report of its occurrence should be made to the Sponsor once the investigator first learns of the event. All related medical records will be required for submission to Hansen Medical for Major Complications that are reported.

All potential Major Complications reported will be reviewed and adjudicated by the CEC. Major Complications will be classified as either a Primary Safety Endpoint or a Chronic Safety Event depending on the event occurrence following the ablation procedure, (Refer to definitions in Sections 5.2 and 5.4).

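### Section 7.8 makes possible association a condition for being an adverse event, so non-serious safety-endpoint events that an investigator judges unrelated can go unrecorded

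*Protocol*

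**What the plan says.** Section 7.8 of the protocol defines an adverse event as "any unfavorable and unintended sign, symptom, or disease possibly associated with the study procedure, study device or required study testing". It then adds: "This does not imply that there is a relationship between the adverse event and the device under investigation". Reporting rests with the site: "The investigator is ultimately responsible for reporting AEs to the Sponsor".

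Section 7.8.3 builds the safety endpoint on that definition: "Major Complications are adverse events which may occur in conjunction with or following atrial ablation". Section 7.7 gives the CEC, among other tasks, review of "all adverse events that have the potential to be Major Complications".

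Other parts of the protocol treat causality as irrelevant to whether an event is recorded:

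- Section 5.2 lists the Major Complications (death, stroke, hospitalization or emergency room visit, and others) with no relatedness condition, and states: "All adverse events will be documented and collected once the informed consent has been signed".
- Section 7.8.2 defines a serious adverse event as any untoward medical occurrence meeting a seriousness criterion, and requires all of them on the eCRF within 24 hours. An overnight observational admission of less than 24 hours is excluded.
- Table 11 records death as an outcome whether or not the event is related to device or procedure.
- Table 12 has a Not related class: "The event is not associated with the investigational device or the procedure described in this protocol".

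**The concern.** The words on possible association act as an entry condition. The investigator applies them before anything is recorded, and so before independent adjudication. The sentence that follows disclaims a relationship to the device only. It does not lift the condition for the procedure or the required testing.

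Taken literally, the adverse event set is narrower than the serious subset it should contain, and narrower than the endpoint list in 5.2. A site that follows 7.8 to the letter could leave out an endpoint component because the investigator thinks it unrelated.

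Any such omission lowers the observed complication rate. The primary safety rate is compared with a fixed performance goal of 16%, and there is no control arm in which the same omission would occur. The error can therefore only favour the device.

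**Working it through.** **Step 1. Which events can be lost?** Follow each kind of event through the reporting routes.

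| Event judged unrelated by the investigator | AE under 7.8 read literally? | SAE route (7.8.2)? | Result |
|---|---|---|---|
| Death; admission meeting the SAE criterion | No | Yes, whatever the cause | Captured |
| Stroke | No | Ordinarily yes | Ordinarily captured |
| Emergency room visit without admission | No | Not necessarily | Exposed |
| Observational overnight stay under 24 hours | No | No, expressly excluded | Exposed |

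The last two rows matter because hospitalization or emergency room visit is itself a 5.2 component. They then depend on the separate Major Complication duty in 7.8.3 and on the visit questions in 7.3.5 and 7.3.6. Section 7.8.3 itself describes Major Complications as adverse events.

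**Step 2. When is the condition strongest?** Table 12 allows an event to be possibly procedure-related on timing alone. In days 0–7, where most primary components are counted, timing will usually satisfy the 7.8 condition. In days 8–365 it no longer does. The CEC's named list of components in 7.7 is also limited to 7 days (day 180 for pulmonary vein stenosis and fistula). For most components after day 7, referral rests on 7.8.3 and on the general limb of 7.7, and both are worded in terms of adverse events. Section 7.5 has a similar filter: for subjects who refuse follow-up, it asks sites to collect only study-related events.

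**Step 3. How sensitive is the safety test to lost events?** Inputs: the goal of 16% and the 95% posterior rule (6.1); N from 125 to 250 (6.5). Assumptions: Beta(1,1) prior and fixed N. The priors and the adaptive details are in Appendix M, which is not shown.

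Safety passes with x events if the Beta(1+x, 1+N−x) distribution function at 0.16 is at least 0.95. The largest passing x is 13 at N=125 and 30 at N=250.

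As a check on this set-up, take the planning case in 6.5 (safety 8%, effectiveness 72%, stated success probability 98%) with independent endpoints:

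- N=125: safety 0.8737 × effectiveness 0.9955 (at least 77 successes) = 0.870.
- N=250: safety 0.9897 × effectiveness 1.0000 (at least 148 successes) = 0.990.

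The stated 98% lies between these values, and nothing suggests it is wrong.

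Now set the true rate at 16%, where passing is a false success on safety, and let a share f of events go unrecorded. The recorded rate is 0.16 × (1−f), and the chance of passing is the binomial probability of at most 13 (or 30) events.

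| f (assumed) | Recorded rate | Pass, N=125 | Pass, N=250 |
|---|---|---|---|
| 0% | 16.0% | 5.1% | 4.7% |
| 5% | 15.2% | 8.1% | 9.0% |
| 10% | 14.4% | 12.3% | 16.1% |
| 20% | 12.8% | 25.8% | 39.7% |
| 30% | 11.2% | 45.8% | 69.9% |

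At N=125 a 10% loss is 2 of an expected 20 events (125 × 0.16 = 20). At N=250 it is 4 of 40.

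**The case against.** The strongest reply is that the protocol does not leave capture to the 7.8 sentence:

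- Serious events are reported whatever the cause.
- Section 7.8.3 requires a Major Complication to be reported promptly, with no causality test.
- Pre-discharge, the scripted day-7 call and later visits ask about Major Complications separately from adverse events.
- A core laboratory reads pulmonary vein imaging.
- Appendix A lists further events to be reported without a causality condition.
- Section 12.4 plans 100% monitoring.

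Most of this stands, and it rules out several stronger readings that a reader might infer:

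- *The investigator's opinion decides whether any endpoint event is ever recorded or reaches the CEC.* Not supported, given the routes above.
- *Late strokes and hospitalizations are the events at risk.* These would ordinarily be serious and so captured. Only the short observational stay is carved out.
- *The Not related class could never be used.* It refers to device and procedure only, whereas 7.8 also covers required testing. An event due to testing alone fits both.
- *The endpoint is confirmed as all-cause.* Section 5.2 has no relatedness condition, but the component definitions are in Appendix L, which is not shown.
- *A true 12% recorded as 10% shows the harm.* The pass probability does rise, from 35% to 63% at N=125 and from 55% to 88% at N=250, but at a true 12% passing is the correct decision.

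The reply does not close the gap entirely. The collection rule in 5.2 and the general limb in 7.7 both use the term adverse event and so inherit its definition. Monitoring checks sites against the protocol's own definition and cannot correct it.

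**Conclusion.** The inconsistency is real and should be corrected, but its reach is narrow. It affects non-serious endpoint components that an investigator judges unrelated and also does not treat as Major Complications. The exposure is greater for the day 8–365 chronic safety rate, which 6.3 reports with a confidence limit and no test, than for the primary rate, where timing alone usually meets the condition.

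The direction is certain: a lost event lowers the rate. The size cannot be derived from the documents. The rise in false success on safety from about 5% to 12% (N=125) or 16% (N=250) rests on an assumed 10% loss of primary endpoint events, a flat prior, fixed N and a true rate of exactly 16%. It shows that the test is sensitive to small losses. It is not an estimate of bias in this trial.

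**What to change.** - In 7.8, define an adverse event as any untoward medical occurrence in a subject after consent, whether or not considered related to the device, the procedure or required testing.
- In 7.8.3, state that every event matching a 5.2 term is entered and sent to the CEC regardless of the investigator's view of causality.
- Keep Table 12 as an attribute recorded for each event, not a condition for recording it.
- Bring 7.5 into line, and reconcile Table 13 with the new statement: its do-not-report list includes some pericarditis and AV block, while pericarditis and heart block are 5.2 terms.

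The cost is a few sentences, site retraining and some additional adverse event entries. No analysis or sample size changes.

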7.8.1 Anticipated Adverse Events

Procedure and device-related complications that may be anticipated in subjects undergoing electrophysiology ablation treatment are listed in Section 8.1. under the risk management section. These pre-defined complications are considered anticipated AEs.

Additionally, adverse events that are inherent to an interventional procedure and expected to occur in most subjects for a projected duration according to the opinion of the investigator may be considered unavoidable. Such events include, but are not limited to, those listed in Table 13. ***Such adverse events that are considered expected and unavoidable to the study (ablation) procedure should not be reported during the study.***

Table 13: DO NOT REPORT: Adverse events related to the initial ablation

Description of the Event	Time Frame from the Index Procedure
Anesthesia-related nausea and/or vomiting.	Resolved within 48 hours with or without antiemetics.
Headache related to NPO status.	Resolved within 24 hours with or without pain medication.
Back pain related to laying on table.	Resolved within 48 hours with or without pain medication.
Pain at access site.	Resolved within 72 hours with or without pain medication.
Sleep problems or insomnia.	Resolved within 72 hours with or without sleeping medication.
Mild to moderate bruising or ecchymosis at access site.	Resolved within 7 days post procedure.
Vaso-Vagal reaction with access site introducer sheath removal.	Reversed with fluid bolus and/or atropine administration.
Self-limiting pericarditis attributable to the ablation procedure defined as pleuritic chest discomfort with or without pericardial rub and ECG changes which did not require prolonged hospitalization.	Physician discretion
Nodal dysfunction rhythms (sick sinus syndrome, sinus bradycardia, sinus arrest or AV blocks) that resulted in symptomatic bradycardia, unrelated to the ablation procedure or pre-existing disease states, treated with pacemaker implantation	N/A
Recurrent AF is not considered an AE. If recurrent AF triggers an event considered to be an AE (hospitalization >24hrs, stroke, etc.) then that event will be documented on the AE case report form.	N/A

7.8.2 Serious Adverse Events (SAEs):

A Serious Adverse Event is any untoward medical occurrence that:

1. Results in death,
2. Is life-threatening,
3. Requires hospitalization or prolongation of existing hospitalization *,
4. Results in persistent or significant disability/incapacity,
5. Requires medical or surgical intervention to prevent serious outcome.

**An observational, overnight hospital admission < 24 hours in duration does not qualify as a SAE.*

All serious adverse events must be reported by eCRF (entering the information into the study electronic database) by the investigator or their designee within 24 hours of receiving the report. The investigator should follow all unresolved serious adverse events until the events are resolved, the subject is lost to follow-up, the subject has withdrawn

consent, or the adverse event is otherwise explained. Investigators also are required to inform their IRB/EC of serious adverse events (as outlined in their IRB/EC procedures) and in accordance with FDA and local regulatory requirements. All related medical records will be required for submission to Hansen Medical for serious adverse events reported.

Any death or atrio-esophageal fistula shall be reported to the FDA by Hansen Medical no later than 10 working days from Hansen Medical's original receipt of the information.

The Hansen Medical contact for questions is:

[name]
Project Lead, Senior Clinical Research Associate
[contact]
E-mail: [contact]

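### The do-not-report list (Table 13) includes pacemaker-treated bradycardia unrelated to the ablation, which the SAE rule and Appendix A require sites to report; no rule says which prevails

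*Protocol*

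**What the plan says.** Section 7.8.1 introduces Table 13 as a list of events that come with this kind of intervention, those "expected to occur in most subjects for a projected duration according to the opinion of the investigator may be considered unavoidable". The instruction is emphasised in the text: "Such adverse events that are considered expected and unavoidable to the study (ablation) procedure should not be reported during the study". The table is titled "DO NOT REPORT: Adverse events related to the initial ablation".

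Two rows matter here.

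- **Pacemaker row.** It names sick sinus syndrome and sinus bradycardia and continues: "sinus arrest or AV blocks) that resulted in symptomatic bradycardia, unrelated to the ablation procedure or pre-existing disease states, treated with pacemaker implantation". The time-frame column says N/A.
- **Pericarditis row.** It covers self-limiting pericarditis attributable to the ablation, described as "pleuritic chest discomfort with or without pericardial rub and ECG changes which did not require prolonged hospitalization". The time frame is left to the physician.

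Section 7.8.2 then sets the SAE rule. The definition opens "A Serious Adverse Event is any untoward medical occurrence that" and lists five criteria. The third is hospitalization or its prolongation, with a footnote exempting observational overnight stays under 24 hours. The fifth is "Requires medical or surgical intervention to prevent serious outcome". The duty is general: "All serious adverse events must be reported by eCRF", within 24 hours.

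Appendix A says that its listed events must be reported throughout the study, and one of them is need for a permanent pacemaker. Section 5.2 names Heart Block, Pericarditis, and Hospitalization or Emergency Room Visit among the primary safety components through day 7, with definitions in Appendix L. Section 7.7 sends the Clinical Events Committee (CEC) every adverse event that could be a Major Complication, and section 7.8.3 requires Major Complications to be reported promptly.

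**The concern.** A site that sees a subject receive a pacemaker for symptomatic AV block, and judges it unrelated to the ablation, has two opposite written instructions. Table 13 says not to report it. Section 7.8.2 and Appendix A say to report it. Sites may therefore handle the same event differently, and the deciding judgement (unrelated) is made by the unblinded investigator before any independent review.

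The first stake is completeness of serious-event reporting. The second is the safety endpoint. Under section 5.2 the CEC adjudicates Major Complications as the investigator reports them, and this is a single-arm trial tested against a fixed 16% goal, so there is no control arm in which under-reporting could offset. If an unreported event would have counted, its loss favours the device. The same holds for the chronic safety endpoint over days 8 to 365 (section 5.4).

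**Working it through.** No figure in the protocol is in dispute, so the main check sets the passages side by side.

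**Pacemaker row against its own table.** The title is limited to events related to the initial ablation; the row is limited to events unrelated to it. The lead-in is limited to events that most subjects will have for a projected time; the row describes a device implant and gives no time frame. The row meets neither condition for being in the table.

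**Pacemaker row against section 7.8.2.** The SAE definition has no causality limit. Symptomatic bradycardia that leads to an implant plausibly meets the fifth criterion (intervention) and often the third (hospitalization). The footnote on stays under 24 hours bears only on the third. The reporting duty has no exception for Table 13, and Table 13 has none for SAEs. By contrast, the recurrent-AF row in the same table does keep serious consequences reportable, so the omission in the pacemaker row is not a convention of the table.

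**Pacemaker row against Appendix A.** The pacemaker entry there covers bradycardia that is chronic, intolerable or thought irreversible and needs a permanent pacemaker. It states no causality condition.

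**Pericarditis row.** It excludes cases with prolonged hospitalization, so on its face it does not breach the SAE duty. Appendix A mentions pericarditis only as an example under infection. What is left is an overlap with the component name in sections 5.2 and 7.7.

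**Heart Block.** Appendix A, which supplements Appendix L, lists only first- or second-degree block that needs no treatment. This suggests that treated block is left to Appendix L, but does not prove it.

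**Direction and scale.** Each subject whose only primary safety event goes unreported lowers the observed rate by 1/125 = 0.8 percentage points at the minimum sample size, or 1/250 = 0.4 points at the maximum.

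An illustration shows whether one such subject could matter. The inputs from section 6.1 are the 16% goal and the requirement that at least 95% of the posterior lie below it. The assumptions are a Beta prior (the design appendix, M, is not shown), fixed N, a true rate of exactly 16%, and exactly one lost endpoint subject. The cut-off c is the largest count x with P(rate < 0.16 | x, N) ≥ 0.95. The chance of passing the safety test is P(X ≤ c) with full reporting and P(X ≤ c + 1) with one subject lost, where X is binomial (N, 0.16).

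| Assumed prior | N | c | Full reporting | One lost |
|---|---|---|---|---|
| Beta(1,1) | 125 | 13 | 5.1% | 8.6% |
| Beta(1,1) | 250 | 30 | 4.7% | 6.8% |
| Beta(2,2) | 125 | 12 | 2.8% | 5.1% |
| Beta(2,2) | 250 | 29 | 3.1% | 4.7% |

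These figures concern the safety test alone; study success also needs effectiveness, and the adaptive design is not modelled. They show direction, not an estimate of the effect in this trial.

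**The case against.** **Causality.** Section 7.8 defines an adverse event as one possibly associated with the procedure, device or testing. On that reading an unrelated pacemaker is not an adverse event at all, and Appendix A, which defines adverse events, would not reach it either. The point is arguable for Appendix A. It fails for SAEs, whose definition has no such limit, and Table 12 provides a Not related category, so the protocol expects unrelated events to be recorded.

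**Endpoint.** A reader might infer that Table 13 removes Pericarditis and Heart Block from the primary safety endpoint and so biases the test. The document does not support that. Section 5.2 gives only names, and Appendix L, which is not shown, may set severity limits that match the rows. A reader might also take both rows to breach the SAE duty; only the pacemaker row does.

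**Other capture routes.** A pacemaker implanted on readmission within 7 days could reach the CEC as Hospitalization or Emergency Room Visit. Major Complications are also asked about at discharge and at the day-7 call (sections 7.3.5 and 7.3.6), and monitoring is 100% (section 12.4). These safeguards are real but partial: staff applying them may still follow Table 13, and adjudication starts from the investigator's report.

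**Frequency.** The pacemaker row is narrow, and the protocol gives no rate for such events. This stands, and it is why no overall size is claimed.

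**Conclusion.** The pacemaker row is a genuine internal contradiction: with its own title and lead-in, with the SAE duty and, on the plain reading, with Appendix A. No passage shown says which instruction prevails. This conclusion does not depend on Appendix L.

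The overlap of the pericarditis row with Pericarditis, and of the pacemaker row with Heart Block, is secondary. It is a question to check against Appendix L, not an established loss of endpoint events. Any effect on the rate tested against 16% can only be downward or nil. Its size is unknown, and for the primary endpoint it may be nil if Appendix L carries the same limits. The point should be fixed because it concerns serious-event reporting and is cheap to settle; the numerical illustration is not the reason.

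**What to change.** Reconcile Table 13 with sections 7.7, 7.8.2 and 7.8.3 and with Appendix A.

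1. Remove the pacemaker row. It does not fit the table's title or lead-in, so a precedence rule alone would leave a confusing entry.
2. Add one sentence to section 7.8.1: *Table 13 does not apply to any SAE, any Appendix A event that must be reported, or any potential Major Complication; these are always reported, and the CEC decides potential Major Complications under Appendix L.*
3. Check the pericarditis row against Appendix L, and keep it only subject to that sentence.

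The change affects reporting only. It costs a table edit, a memo to sites, and a few more reports and adjudications. The observed complication rate may rise slightly.
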